
Primary Safety Endpoint
	
Freedom from the following Major Adverse Events (MAEs) through a 30-day follow-up period, as adjudicated by the Clinical Event Committee (CEC):
 
 Unplanned target limb amputation above the ankle Clinically Driven Target Lesion Revascularization (CD-TLR) Cardiovascular related deaths 
This endpoint will be met if the freedom from MAE rate is greater than 85%

Secondary Safety Endpoints
	
Freedom from the following Clinically Significant Device Related Adverse Events requiring intervention in the target vessel, as adjudicated by the CEC for up to 30 days:
 
 • Perforation • Dissection • Distal embolization or in situ thrombus • Pseudoaneurysm 
Freedom from non-Clinically Significant Device Related Adverse Events in the target vessel, as adjudicated by the CEC for up to 30 days:
 
 • Perforation • Dissection • Distal embolization or in situ thrombus • Pseudoaneurysm

Secondary Effectiveness Endpoints
	
Percent of subjects with residual stenosis by angiography of ≤ 30% post-procedure including any adjunctive therapy, with no flow limiting dissection, as adjudicated by the core laboratory.

Safety and Effectiveness Evaluation of Eximo Medical's B-Laser™ atherectomy Device, in Subjects Affected with Infrainguinal PAD

Date:
02 Oct 2017

PRODUCT: Eximo Medical B-Laser™ for PAD

Page 3 of 5

Document number: EX-PAD-03

Revision: 02

	
PAD measurements at the 30-day visit post-procedure compared to baseline:
 
• Ankle-Brachial Index (ABI)• Rutherford Classification• Walking Impairment Questionnaire (WIQ) 
Clinical success at 30 days defined as < 50% stenosis at the treated lesion, as assessed quantitatively by duplex ultrasound by the core laboratory when the peak systolic velocity ratio is < 2.5. ¹

Statistical Methodology	
Primary Effectiveness	The primary effectiveness endpoint is the reduction from baseline in residual diameter stenosis (measured in percent), prior to any adjunctive therapy, achieved by the B-Laser™ catheter, as assessed quantitatively by the core laboratory based upon the procedure angiograms. This study's primary effectiveness endpoint will be met if the mean reduction in residual diameter stenosis is greater than 20%, prior to any adjunctive therapy.

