Statistical Hypothesis	The primary effectiveness hypothesis to be tested is: $H_0: \mu_{DS} \leq 20\% \text{ vs. } H_1: \mu_{DS} > 20\%$ where μ_{DS} is the mean reduction from baseline in residual diameter stenosis.
Statistical Test	The hypothesis will be tested using Analysis of Covariance (ANCOVA)
Minimum Sample Size	97 treated subjects (assuming one lesion per subject)
Primary Safety	The primary safety endpoint is the percent of subjects free of MAEs throughout the 30-day follow-up period, as adjudicated by the CEC.
Statistical Hypothesis	The primary safety hypothesis to be tested is: $H_0: \pi_{MAEF} \leq 85\% \text{ vs. } H_1: \pi_{MAEF} > 85\%$ where π_{MAEF} is the proportion of subjects free of MAEs throughout the 30-day follow-up period.
Statistical Test	The hypothesis will be tested via the lower limit of a one-sided exact binomial confidence interval.
Study Population	The trial population will consist of male and female subjects eighteen (18) years of age or older, with symptomatic infrainguinal PAD, scheduled for endovascular intervention. Subjects must also meet all other inclusion criteria and not meet any of the exclusion criteria described in Sections 5.3.1 and 5.3.2 of the Study Protocol.

¹ Per FDA request, PSVR will be presented for any subject that underwent DUS. Yet, in cases when a reference PSV is unreliable, an asterisk will be added, and the meaning of this asterisk is that true PSVR could not be calculated by the core lab and rather the core is presenting a PSVR that is using the best PSV that could be taken. The company will keep in house the records of the alternative determination of patency by the core lab in such cases that are based on correlating factors that will be used to determine stenosis (further information can be found in section 3.1 of the study protocol, PAD diagnosis, Duplex ultrasonography (DUS)).

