6-Month Outcomes Analysis (from Day 36 to the end of study)	
The follow-up duration for each subject is 30-days post procedure for the primary and secondary endpoints, however subjects will be followed for 6-months post procedure.
 
At follow up visits the following parameters will be collected and recorded:
 
 • 6-Month Patency (per Lesion): Duplex Ultrasonography for core lab assessment of PSVR< 2.5. • 6-Month Clinical Presentation (per Subject): Clinical performance by Rutherford Class, ABI and WIQ • 6-Month Site-Reported Adverse Events & Serious Adverse Events • 6-Month CEC-Adjudicated Adverse Events • 6-Month Protocol Deviations 
All parameters measured after the 30-day follow-up (from Day 36 after procedure) will be summarized via descriptive statistics by data type.
				
	Visit, Number, (Time point)	Screening Visit 1 (<2m pre-procedure)	B-Laser™ procedure Visit 2 (to discharge)	Follow up Visit 3 (30d ± 5d post procedure)	Follow up Visit 4 (6m ± 2w post procedure)
	Informed consent	X			
	Assess eligibility	X			
	Medical history & demographic	X			
	Blood Tests	X			
	Con-meds	X	X	X	X
	Baseline lesion evaluation	X	X		
	Short Physical examination	X			
	Ankle-Brachial Index	X		X	X
	Rutherford Classification	X		X	X
	WIQ	X		X	X
	& Confirm eligibility per intraoperative inclusion/exclusion		X		
	PAD Intervention including B-Laser™ Atherectomy		X		
	Safety- AE, SAE, MAE, ADE		X	X	X

Safety and Effectiveness Evaluation of Eximo Medical's B-Laser™ atherectomy Device, in Subjects Affected with Infrainguinal PAD

Date:
02 Oct 2017

PRODUCT: Eximo Medical B-Laser™ for PAD

Page 5 of 5

Document number: EX-PAD-03

Revision: 02

Results	
Primary Effectiveness Results At baseline, the mean (SD) percent stenosis at the target lesion was 85.7% (12.2%). Post B-Laser™ prior to adjunctive therapy, the mean (SD) percent stenosis at the target lesion was 52.1% (14.9%). This resulted in a crude mean (SD) reduction from baseline to post B-Laser™ of 33.6% (14.2%).
 
Primary Safety Results The freedom from MAE through the 30-day follow-up period after intervention was 98.9%, with a lower limit of the one-sided 97.5% exact binomial confidence interval of 94.2%, which is greater than the pre-specified threshold of 85%, so the success criteria for this endpoint is met.

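### As written in this summary, 30-day clinical success and 6-month patency carry no condition on target lesion revascularisation, so a lesion re-treated before the scan and then open meets both definitions (minor point)

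*Combined protocol and SAP*

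**What the plan says.** Two outcomes in the combined protocol and SAP summary rest on the duplex scan.

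- **30 days.** The Secondary Effectiveness Endpoints row has "Clinical success at 30 days defined as < 50% stenosis at the treated lesion, as assessed quantitatively by duplex ultrasound by the core laboratory", tied to a peak systolic velocity ratio (PSVR) below 2.5.
- **6 months.** The 6-Month Outcomes Analysis row lists "6-Month Patency (per Lesion): Duplex Ultrasonography for core lab assessment of PSVR< 2.5" among the parameters to be recorded at follow-up. They are summarised descriptively. The same row places them outside the formal endpoints: "The follow-up duration for each subject is 30-days post procedure for the primary and secondary endpoints".

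Footnote 1, marked at the 30-day endpoint, says that "PSVR will be presented for any subject that underwent DUS". Where the reference velocity is unreliable, it provides for an "alternative determination of patency by the core lab in such cases", based on correlating factors that the summary does not define, and adds that "further information can be found in section 3.1 of the study protocol".

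Revascularisation of the target lesion appears in one place only: clinically driven revascularisation (CD-TLR) is one of three components of the 30-day major adverse event (MAE) endpoint for safety. After 30 days, CEC-adjudicated adverse events are listed as an item separate from patency.

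**The concern.** A patency rate is normally read as the share of treated lesions that stayed open after the study treatment. If a lesion closes, is re-treated and then scans open, its duplex result reflects the second procedure. Under a definition that looks only at the scan, that lesion is a success. Counting it so can raise the rate but cannot lower it, and in a single-arm study no comparator carries the same bias.

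What is at stake is how one secondary endpoint and one descriptive 6-month outcome are interpreted. From the rate alone, a reader could not separate lesions still open after the index treatment from lesions reopened later.

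**Working it through.** **1. Does any other part of the summary remove re-treated lesions?**

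| Place | What it covers | Does it reclassify a re-treated lesion? |
|---|---|---|
| Secondary Effectiveness Endpoints, 30-day clinical success | Core-lab duplex, PSVR below 2.5 | No |
| 6-Month Outcomes Analysis, patency | Core-lab duplex, PSVR below 2.5 | No |
| Footnote 1 | Scans with an unreliable reference velocity; substitutes another core-lab judgement of stenosis | No mention of revascularisation |
| Primary Safety Endpoint | CD-TLR to 30 days | Counted for safety, not linked to lesion status; omits revascularisation that was not clinically driven |
| 6-Month Outcomes Analysis, adjudicated events | Events after the 30-day visit | Listed separately, not linked to patency |
| Exclusion criterion 3 | Procedures planned within 30 days after the index procedure | Does not cover unplanned re-treatment or later procedures |

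Nothing in the summary takes such a lesion out of the numerator.

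**2. Reproducing the one reported figure that includes revascularisation.** Primary Safety Results gives freedom from MAE of 98.9%, with a one-sided 97.5% exact lower limit of 94.2%. Discussion and Conclusions gives one MAE. The denominator n is not stated. For k events in n subjects, the Clopper-Pearson lower limit is the 0.025 quantile of Beta(n − k, k + 1). With k = 1:

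| n | Freedom from MAE | Lower limit |
|---|---|---|
| 92 | 98.91% | 94.09% |
| 93 | 98.92% | 94.15% |
| 94 | 98.94% | 94.21% |
| 95 | 98.95% | 94.27% |

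Only n = 93 and n = 94 round to both reported figures. With k = 2 or 3, no n from 20 to 399 fits both. The reported result therefore agrees with one MAE among 93 or 94 subjects.

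**3. Bound at 30 days.** One MAE, of unstated type, means at most one subject with a CD-TLR. With one lesion per subject, the effect on 30-day clinical success is zero or one lesion: 1/94 = 1.06 points or 1/93 = 1.08 points if all were scanned, and 1/80 = 1.25 points if only 80 were (an assumption). One lesion per subject is stated only for the sample size ("assuming one lesion per subject"), while the inclusion criteria allow more than one target lesion. Two re-treated lesions in that one subject would give 2/94 = 2.13 points. Revascularisation that was not clinically driven is not an MAE, so this bound does not cover it.

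**4. Size at 6 months.** No patency rate, scan count or revascularisation count is given, so the total cannot be computed. Let m be the lesions scanned, S those that scan open, r the re-treated lesions among S, and u the re-treated lesions never scanned.

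- Duplex-only rate: S/m.
- Rate with revascularisation as failure: (S − r)/(m + u).

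The second can never exceed the first. With u = 0, each affected lesion is worth 1/m: 1/97 = 1.03 points to 1/80 = 1.25 points for an assumed m of 80 to 97.

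As an illustration only, assume m = 97 and S = 87, so the duplex-only rate is 89.7%. With u = 0:

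- r = 1: 86/97 = 88.7%
- r = 3: 84/97 = 86.6%
- r = 5: 82/97 = 84.5%
- r = 10: 77/97 = 79.4%

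Unscanned lesions matter too: r = 1 and u = 1 gives 86/98 = 87.8%.

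**The case against.** The strongest reply is that this is an argument from silence in a five-page summary. The summary defers to a full study protocol for duplex details, and that protocol was not supplied. No sentence says how a re-treated lesion is scored. This stands, and it limits the claim to what the summary states. It does not remove the gap, because a reader applying the definitions as written would count such a lesion as a success.

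Second, the 6-month line names something to be recorded and sets no success criterion. Duplex status at a visit is a legitimate descriptive quantity, and the summary never claims patency free of re-intervention. This also stands, and is why the duplex-only rate should be kept beside the stricter one. It does not apply to 30-day clinical success, which is a named secondary endpoint.

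Third, the 30-day effect may be nil. The single MAE may have been a death or an amputation, and it is described as unrelated to the device. For clinically driven events this is right.

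A reader might go further and infer that the sponsor chose to score re-treated lesions as patent, that a reported patency rate is inflated, or that the claim of effectiveness is weakened. The documents support none of these. No scoring rule for re-treated lesions is stated, and no patency or clinical success rate appears. The only 6-month conclusion concerns symptoms. The primary effectiveness endpoint is measured on the procedure angiograms before any adjunctive therapy, so later re-treatment cannot affect it.

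**Conclusion.** The point holds as a minor one on secondary and descriptive outcomes. In the supplied summary, both duplex outcomes lack a revascularisation condition, and the literal definition can only favour the device as a measure of durability.

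At 30 days, the effect of clinically driven events is limited to one subject: zero or about 1 point, given one lesion per subject and a denominator of 93 or 94 inferred from the reported interval. Revascularisation that was not clinically driven is unbounded. At 6 months, only the per-lesion effect can be given, about 1 point for an assumed 80 to 97 lesions scanned.

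Neither primary conclusion changes: CD-TLR already counts as a failure in the safety endpoint. If the full protocol contains a rule for re-treated lesions, citing it settles how they are classified.

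**What to change.** If the full study protocol says how re-treated lesions are classified, cite that section beside both definitions. If it does not:

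- Count any lesion with target lesion revascularisation between the index procedure and the visit as a failure of 30-day clinical success or 6-month patency, whether or not it was later scanned.
- Use as denominator the lesions with an evaluable scan plus those with a prior revascularisation and no scan. Otherwise a lesion that was re-treated and never scanned drops out, and the rate stays too favourable.
- Show the duplex-only rate, with lesions scanned as its denominator, beside it, and give the counts for both.
- Label the tabulation post hoc, because results are already reported.

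The cost is a re-tabulation of duplex and adjudicated event data that the plan already collects, a check of adverse event records for revascularisations that were not clinically driven, and a possibly less favourable descriptive rate. If no lesion was re-treated, the two rates will agree and the question closes.

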Safety and Effectiveness Evaluation of Eximo Medical's B-Laser™ atherectomy Device, in Subjects Affected with Infrainguinal PAD

Date:
02 Oct 2017

PRODUCT: Eximo Medical B-Laser™ for PAD

Page 1 of 5

Document number: EX-PAD-03

Revision: 02

Protocol Number	EX-PAD-03
Title	Safety and Effectiveness Evaluation of Eximo Medical's B-Laser™, an Atherectomy Device, in Subjects Affected with Infrainguinal PAD
Objective(s)	The primary objective of the study is to assess the safety and efficacy of the Eximo Medical's B-Laser™ catheter in subjects with infrainguinal peripheral artery disease (PAD)
Study Design	This is a prospective, single-arm, multi-center, open-label study.
Inclusion Criteria	
1. Subject is \geq 18 years old.2. Subject is a candidate for atherectomy for infrainguinal peripheral artery disease.3. Documented symptomatic atherosclerotic peripheral artery disease Rutherford Classification 2-4.4. Subject has an infrainguinal target lesion(s) with any type of stenosis (naïve recurrent, or in-stent) estimated to be \geq70% based on CT angiogram or any other imaging modality.5. Subject is capable and willing to comply with the scheduled follow up6. Subject or appropriate legal surrogate is able and willing to sign a written Informed Consent Form (ICF). 
Intraoperative inclusion criteria (by fluoroscopy angiogram):
 
1. Target lesion has a stenosis estimated to be \geq70%.2. In ATK subjects - at least one patent tibial run-off vessel into the foot

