Discussion and Conclusions	
The aim of the study was to assess the safety and efficacy of the use of the Eximo Medical's B-Laser™ catheter in subjects affected with infrainguinal PAD. The study was designed to assess both safety and effectiveness of the device, and there were two hypotheses in this study.
 
The primary effectiveness endpoint was the mean reduction from baseline in residual diameter stenosis (measured in percent), prior to any adjunctive therapy, achieved by the B-Laser™ catheter, as assessed quantitatively by the core laboratory based upon the procedure angiograms. Because the lower limit of the one-sided 97.5% confidence interval was greater than 20%, we conclude that the mean reduction from baseline in diameter stenosis is > 20% prior to any adjunctive therapy, and the success criterion for this endpoint is met.
 
The primary safety endpoint is the percent of subjects free of MAEs throughout the 30-day follow-up period, as adjudicated by the Clinical Events Committee (CEC). This hypothesis was tested via the lower limit of the one-sided 97.5% exact binomial confidence interval. Because the lower limit of the confidence interval was greater than 85%, this endpoint is met.
 
Thus, the study is deemed successful as both null hypotheses (primary efficacy and primary safety endpoints) were rejected and the acceptance criteria were met. It can be claimed that Eximo Medical's B-Laser™ device is safe and effective according to its intended use.
 
The results found were quite robust. There did not appear to be statistically significant differences in the primary effectiveness endpoint across centers ($p=0.3071$) and there was only 1 non-device related MAE though 30 days, suggesting a very strong safety profile.
 
The 6-month observational outcomes showed a global improvement of the peripheral artery disease symptoms.
 
An independent Data and Safety Monitoring Board has also reviewed and evaluated the results and affirmed that based on the information that the committee was provided, the device is safe for its intended use.

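### Does the primary safety result rest on fewer subjects than the planned minimum of 97?

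*Combined protocol and SAP*

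**What the plan says.** The primary safety analysis is per subject. The Primary Safety row of the Statistical Methodology states: "The primary safety endpoint is the percent of subjects free of MAEs throughout the 30-day follow-up period". The test compares the lower limit of a one-sided exact binomial confidence interval with 85%. The safety rows give no sample size.

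The only sample size in the document is in the primary effectiveness rows: "97 treated subjects (assuming one lesion per subject").

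The Results section reports that freedom from MAE "was 98.9%, with a lower limit of the one-sided 97.5% exact binomial confidence interval of 94.2" percent and concludes that the criterion is met. The Discussion adds that "there was only 1 non-device related MAE though 30 days". The document does not give the number of subjects treated, the number with known 30-day status, or the fraction behind the 98.9%.

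Two other entries bear on how the 97 might be read. The inclusion criteria allow more than one lesion ("Subject has an infrainguinal target lesion(s) with any type of stenosis"), and one 6-month outcome is counted by lesion ("6-Month Patency (per Lesion")).

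**The concern.** A single-arm comparison with a fixed goal has no control group to absorb selective loss, so the result is only as good as its denominator. Here the denominator can be recovered from the printed figures, and it is smaller than the only sample size stated. A reader would ask three things:

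- Were some treated subjects left out of the safety analysis, for example because their 30-day status was unknown?
- Were fewer than 97 subjects treated?
- Was 97 in effect a lesion count, given its one-lesion-per-subject condition?

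Under the first reading, the printed rate describes evaluable subjects and not all treated subjects. The difference could go either way: event-free absent subjects would raise the result slightly, and absent subjects with MAEs would lower it. If enough were absent, the comparison with 85% could be in doubt. The Discussion also says "The results found were quite robust", which might be taken as an assurance on this point.

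**Working it through.** **Inputs.** Rate 98.9% and lower limit 94.2% at one-sided 97.5% (Results, Primary Safety); one MAE (Discussion); goal 85% (Primary Safety hypothesis); 97 treated subjects (Minimum Sample Size, effectiveness rows).

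**Formula.** For x event-free subjects out of n, the exact (Clopper-Pearson) one-sided 97.5% lower limit is the 0.025 quantile of a Beta(x, n − x + 1) distribution.

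**Step 1: reproduce the printed result.** With one MAE, x = n − 1:

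| x/n | Rate | Lower limit | Prints as 98.9% / 94.2%? |
|---|---|---|---|
| 91/92 | 98.91% | 94.09% | no (94.1%) |
| 92/93 | 98.92% | 94.15% | yes |
| 93/94 | 98.94% | 94.21% | yes |
| 94/95 | 98.95% | 94.27% | no (94.3%) |
| 96/97 | 98.97% | 94.39% | no (99.0% / 94.4%) |

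A search over n from 10 to 999 with 0 to 11 events finds no other match under ordinary rounding. If the figures were truncated instead, 93/94 and 94/95 would fit. The implied denominator is therefore 97 − 94 = 3 or 97 − 93 = 4 below 97 under rounding, and 2 or 3 below under truncation. The printed result agrees with the reported single MAE, so it contains no arithmetic error.

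**Step 2: worst case at the stated size.** Assume exactly 97 were treated and count every absent subject as an MAE:

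- 93 evaluable: 4 absent, 92/97 = 94.8%, lower limit 88.4%.
- 94 evaluable: 3 absent, 93/97 = 95.9%, lower limit 89.8%.

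Both limits exceed 85%. In general, 97 subjects can carry up to 7 MAEs and still pass (90/97, limit 85.7%); 8 MAEs fail (89/97, limit 84.4%).

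**Step 3: how many missing subjects it would take.** The number treated is not stated, so it is varied here as an assumption. Worst-case lower limits:

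| Treated | 93 evaluable (x = 92) | 94 evaluable (x = 93) |
|---|---|---|
| 97 | 88.4% | 89.8% |
| 98 | 87.1% | 88.5% |
| 99 | 86.0% | 87.3% |
| 100 | 84.8% | 86.1% |
| 101 | – | 84.99% |

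With up to 6 missing (99 or 100 treated), no pattern of outcomes overturns success. With 7 missing (100 or 101 treated), the limit falls just below 85% only if all 7 had MAEs.

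**Step 4: best case.** If 97 were treated and all absent subjects were event-free, 96/97 gives 99.0% with a limit of 94.4%, barely different from the printed result.

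**Step 5: the other two readings.** If fewer than 97 were treated, or if 97 was a lesion count (97/94 = 1.03 or 97/93 = 1.04 lesions per subject), and nobody was missing, the safety figures stand as printed.

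**The case for a change.** The best case for asking for a change is that a treated subject would ordinarily count towards 30-day safety, whichever endpoint set the sample size. A safety denominator below a minimum of treated subjects therefore needs a sentence of explanation. Because 97 is a minimum, the true number treated could be higher, and from 100 or 101 upwards the extreme worst case falls below 85%. A document that reports a result and declares success could print the fraction at almost no cost.

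The request for the fraction and the number treated is reasonable as reporting, and it stands. The rest carries less weight. Nothing in the document suggests that 100 or more were treated, and 7 MAEs among 7 absent subjects would contrast sharply with 1 among the 93 or 94 observed. Asking that safety be based on every subject in whom the device was used presumes an exclusion that has not been shown. The robustness remark in the Discussion is explained by its next sentence, on differences between centers and the single MAE; it makes no claim about missing data.

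Filling unknown 30-day status from later data is less certain than it may look. The item "6-Month CEC-Adjudicated Adverse Events" is listed under outcomes from Day 36 onwards. Such data would help only where they also cover days 0 to 30, and a subject lost early may have no 6-month visit.

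Finally, this is a five-page summary that refers to a separate Study Protocol. Disposition and analysis sets may be set out elsewhere.

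**Conclusion.** The concern does not call for a change. The back-calculation is sound: under ordinary rounding the safety denominator is 93 or 94, and the document does not explain the gap from 97. But the two numbers measure different things. One is a planned minimum of treated subjects for effectiveness; the other is an inferred count for the 30-day safety analysis. Both can be true together, and no wrong figure, rule or analysis is shown.

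The safety conclusion does not depend on the gap at the only size stated. With 97 treated and all absent subjects counted as MAEs, the lower limit is 88.4% or 89.8% against a goal of 85%. This assumes exactly 97 treated and conventional rounding. Up to 6 missing subjects could not reverse it under any pattern of outcomes. What remains is a detail of reporting that an analyst holding the disposition table would supply as a matter of course: the fraction, the number treated, and the reason for any difference.
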